**Table 1: Baseline and demographic characteristics**

### ***G. Statistical Plan and Sample size estimation***

Analyses will be modified intent-to-treat, including all randomized patients who received treatment (i.e., patients randomized but not receiving treatment will not be included in the analyses). The treatment groups will be compared on baseline characteristics using absolute standardized difference (ASD), defined roughly as the absolute difference in means divided by the pooled standard deviation. Imbalance will be defined as an ASD of greater than 0.10. All the analyses will be adjusted for imbalanced baseline characteristics. The confidence level for all analyses is set at 95% ( $p < 0.05$ )

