#### **Primary Analysis**

The effect of pre-operative patient education on cumulative opioid consumption (morphine equivalents) during first 72 postoperative hours will be assessed by using a t-test on the log transformed opioid consumption. Linear regression will be used to adjust for imbalance if necessary. The 95% CI for the ratio of geometric means (intervention/placebo) between the two groups will be reported.

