#### **Secondary Analysis**

The effect of the intervention on patient quality satisfaction scores assessed on the third post-operative day will be determined by using a t-test or linear regression adjusting for imbalanced covariates as appropriate. If the distribution of patient satisfaction scores is skewed, we will use Wilcoxon rank-sum test or log-transformed scores to assess the effect.

The effect on time-weighted average pain scores during the first 72 post-operative hours will be assessed in a manner similar to that for patient satisfaction scores.

Adjusting for multiple testing using the Bonferroni correction, the secondary analyses will be carried out at the 97.5% confidence level (i.e.  $p < 0.05/2$ ).

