## **Interim Analysis**

Three interim analyses will be conducted at 25%, 50% and 75% of the planned enrollment to assess efficacy utility using a group sequential design with a gamma spending function (Gamma = -4 for efficacy and Gamma = -1 for futility) with non-binding efficacy and futility boundaries. The probability of crossing either the efficacy or futility boundary at the first, second and third interim analysis will be 9%, 40% and 78% respectively if the alternative hypothesis is true.

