### ***H. Sample Size Calculations***

The coefficient of variation (CV) for cumulative opioid consumption was estimated to be 1.32 using a previous study. However, for our sample size calculations, we assume a lower CV of 1.00 because--unlike the previous study--we will be excluding patients with a history of opioid use in the past 3 months.

Based on the primary outcome of cumulative opioid consumption during the first 72 post-operative hours and assuming a CV of 1.00 we would need a total of 588 patients to have 90% power to detect a 20% decrease in opioid consumption at the 0.05 significance level. Planning for 3 interim analyses and one final analysis, we would require a maximum of **672 patients**. The boundaries for the analysis [efficacy (futility)] are:  $P \leq 0.002$  ( $P > 0.926$ ),  $P \leq 0.005$  ( $P > 0.624$ ),  $P \leq 0.015$  ( $P > 0.2011$ ), and  $P \leq 0.044$  ( $P > 0.044$ ).

**Internal Pilot Study to Re-assess Variability in Primary Outcome.** The coefficient of variation will be re-assessed via an internal pilot study at 50% of the planned enrollment, and sample size will be increased if needed. For a CV of 1.32 and planning for three interim analyses and one final analysis, we would need a maximum of **974 patients**.

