**Second interim analysis re-assessment:**

Based on the results of the second interim analysis executive committee suggested to increase the sample size to **760 patients** to compensate the technical data loss.

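### The primary test has two stated significance levels (0.05 and 0.044), and the visible text gives no updated final boundary after the maximum rose to 1060

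*Combined protocol and SAP*

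**What the plan says.** - Section G (Statistical Plan and Sample size estimation): "The confidence level for all analyses is set at 95"%, with p < 0.05. No exception is made for the primary outcome.
- Primary Analysis: a t-test on log opioid consumption, and "The 95% CI for the ratio of geometric means (intervention/placebo) between the two groups will be reported". The sequential design is not mentioned.
- Secondary Analysis: "the secondary analyses will be carried out at the 97.5% confidence level". This is the one place in the analysis sections where a departure from the general level is written down.
- Interim Analysis: "Three interim analyses will be conducted at 25%, 50% and 75% of the planned enrollment", using gamma spending (−4 for efficacy, −1 for futility) "with non-binding efficacy and futility boundaries".
- Section H (Sample Size Calculations): 588 patients for a single-look design at CV 1.00, 90% power and a 20% reduction at the 0.05 level. Then "Planning for 3 interim analyses and one final analysis, we would require a maximum of" 672. "The boundaries for the analysis [efficacy (futility)] are" followed by efficacy values 0.002, 0.005, 0.015 and, at the final analysis, 0.044.
- Second interim re-assessment: the maximum goes to 760 "to compensate the technical data loss".
- Third interim re-assessment: with CV 1.30 and 10% drop-out the total becomes 1060, again described as 90% power at a 0.05 level. No nominal final boundary accompanies it. Figure 1, on the boundaries, follows this text; its content was not available for this review.

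**The concern.** There are two problems with the same success rule.

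First, a final p-value of 0.047 is positive under section G and negative under section H. Nothing in section G or in the primary analysis paragraph says which governs, although the secondary outcomes are given their own level explicitly.

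Second, 0.044 is correct only for looks at 25, 50, 75 and 100% of the maximum. The maximum was raised to 1060 after the third look had been taken. Look 3 is therefore no longer at 75% of the information, and the correlation between the interim and final statistics is weaker than the boundary assumed. With the same interim bounds, a final test at 0.044 then spends more than 5% in total.

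At stake is whether a borderline final result counts as success. If that is settled only after the p-value is known, it will look data-driven.

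**Working it through.** **Inputs.** From the plan: overall alpha 0.05, taken as two-sided because that reproduces the printed figures; power 90%; ratio 0.80; CV 1.00, later 1.30; drop-out 10%; looks at 25/50/75/100%; gamma −4; maxima 672, 760 and 1060. Assumed, because the plan does not give them: look sizes of 168 and 336 (25% and 50% of 672), and 504 (75% of 672) or 570 (75% of 760) for look 3; a final analysis of 954 (1060 × 0.9) or 1060 patients.

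**Step 1: reproduce the printed boundary.** Cumulative alpha spent is α(t) = 0.05 × (1 − e^{4t}) / (1 − e^{4}), which gives 0.0016, 0.0060, 0.0178 and 0.0500. Solving the group sequential recursion by numerical integration gives nominal two-sided p-values of 0.0016, 0.0048, 0.0147 and 0.0440, matching section H. So 0.044 is the final nominal level for an overall two-sided alpha of 0.05.

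**Step 2: error at the original timing, futility not enforced.** Ranges run from exact interim bounds to the bounds rounded as printed.
- Final test at 0.044: 5.00–5.04%.
- Final test at 0.05: 5.54–5.58%.

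**Step 3: is the sequential design still in force at 1060?** Use σ² = ln(1 + CV²) and N = 4(1.960 + 1.282)² σ² / (ln 0.8)².
- CV 1.00: N = 585 (588 with the t distribution, as printed).
- CV 1.30: N = 835 (838 with the t distribution).
- With the plan's own inflation: 835.3 × 672/588 = 954.6, and 954.6/0.9 = 1060.7.
- Without inflation: 835.3/0.9 = 928.

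The figure of 1060 therefore retains the inflation for four looks. The design was kept, and it needs a final level.

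**Step 4: where look 3 now falls.** 504/1060 = 0.48, 504/954 = 0.53, 570/1060 = 0.54, 570/954 = 0.60. The boundary assumed 0.75.

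**Step 5: error after the step to 1060, with the section H bounds used at looks 1–3 and futility not enforced.**

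| Look 3 / final N | Error at 0.044 | Error at 0.05 | Final level restoring 5% |
|---|---|---|---|
| 504 / 954 | 5.39–5.44% | 5.94–5.99% | 0.0397–0.0391 |
| 504 / 1060 | 5.48–5.53% | 6.03–6.08% | 0.0388–0.0382 |
| 570 / 954 | 5.32–5.37% | 5.87–5.91% | 0.0404–0.0399 |
| 570 / 1060 | 5.42–5.47% | 5.97–6.02% | 0.0394–0.0388 |

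A simulation of 2 million trials (printed bounds, 168/336/570/1060) agrees: 5.47% at 0.044, 6.02% at 0.05 and 4.99% at 0.0388.

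**Step 6: sensitivity to what was actually done.**
- Step to 760 alone, final at 0.044: 5.04–5.08% with look 3 at 570, and 5.16–5.21% with look 3 at 504. Little effect.
- Look 3 re-spent against 760: the restoring level is 0.0427–0.0434 if look 3 was at 504, and 0.0397–0.0408 if at 570. Error at 0.044 is 5.06–5.12% and 5.29–5.39% respectively.
- All three looks re-spent against the new maximum: the restoring level is 0.0462–0.0474, and error at 0.044 is 4.67–4.79%. This is not what the plan describes, since 1060 was set only after look 3.
- Printed futility bounds always obeyed: error stays below 5%, at 3.8–4.4% with 0.044 and 4.1–4.8% with 0.05. The plan makes those bounds non-binding, so this cannot be relied on.

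**The case against.** The strongest reply is that section G is a general default and section H is the specific rule for the primary outcome. Specific text normally governs, and 0.044 is exactly what an overall 0.05 yields. On that reading nothing is wrong at the original timing except a missing cross-reference. This is the sensible reading and is accepted here. It does not make the text say so, and the third re-assessment repeats 0.05 without a nominal boundary, which adds to the ambiguity.

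A conventional 95% interval after a sequential test is common practice and is not an error in itself. That stands, provided the interval is not used to declare success.

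Figure 1 may already carry updated boundaries. That is possible, so the second half of this point is limited to the visible text.

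The look sizes and interim bounds actually used are not in the plan, and the restoring level ranges from 0.038 to 0.047 across the scenarios. That also stands: 0.038–0.040 is conditional and should not be adopted without the real figures.

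Finally, 0.044 would remain valid with a statistic weighted in advance by the original information fractions. True, but the plan names an ordinary t-test and specifies no such weighting.

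**Conclusion.** The point holds and should be fixed. The success threshold for the primary hypothesis is stated in two ways, and the printed 0.044 rests on a look 3 timing that the step to 1060 no longer satisfies.

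The size is modest. Literal use of section G adds about half a percentage point of type I error under the original design. After the step to 1060, keeping 0.044 adds about 0.3–0.5 points and using 0.05 adds about 0.9–1.1 points. These later figures assume the printed bounds at looks 1–3, an ordinary pooled final test, futility not enforced, and a new maximum that did not depend on the observed treatment difference. Under those assumptions only a final p between about 0.038 and 0.05 would be read differently.

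Confidence is high on the wording conflict. The exact replacement level depends on look sizes and interim bounds that the plan does not state.

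**What to change.** 1. In section G and the primary analysis paragraph, state that 0.05 is the overall two-sided alpha and that the primary outcome is judged against the group sequential boundary.
2. In section H and the third re-assessment, record the actual number of patients at each look and the interim bounds actually used.
3. Replace 0.044 with the final nominal level recomputed from the alpha already spent and the actual information fractions. As an illustration, this is about 0.038–0.040 under the assumptions of step 5; other look sizes or bounds give a different value. If Figure 1 already shows updated boundaries, cite it and print the value in the text.
4. Either label the 95% interval as unadjusted and not the basis for declaring success, or report an interval at the matching level (for example 1 − 0.040 = 96.0% to 1 − 0.038 = 96.2% in the illustrated case).

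All of this should be fixed in writing before the final analysis.

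Cost: some wording and one boundary calculation, with no extra patients. In the illustrated case, power of the final test at 954 evaluable patients, CV 1.30 and ratio 0.80 goes from 0.9265 at 0.044 to 0.9208 at 0.040 or 0.9176 at 0.038, a loss of less than one percentage point.

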#### **Primary Analysis**

The effect of pre-operative patient education on cumulative opioid consumption (morphine equivalents) during first 72 postoperative hours will be assessed by using a t-test on the log transformed opioid consumption. Linear regression will be used to adjust for imbalance if necessary. The 95% CI for the ratio of geometric means (intervention/placebo) between the two groups will be reported.

#### **Secondary Analysis**

The effect of the intervention on patient quality satisfaction scores assessed on the third post-operative day will be determined by using a t-test or linear regression adjusting for imbalanced covariates as appropriate. If the distribution of patient satisfaction scores is skewed, we will use Wilcoxon rank-sum test or log-transformed scores to assess the effect.

The effect on time-weighted average pain scores during the first 72 post-operative hours will be assessed in a manner similar to that for patient satisfaction scores.

Adjusting for multiple testing using the Bonferroni correction, the secondary analyses will be carried out at the 97.5% confidence level (i.e.  $p < 0.05/2$ ).

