#### ***Secondary Aims***

*Secondary Aim 1:* To assess whether patients assigned to analgesic education (versus standard/generic) have better patient satisfaction with post-operative pain management.

Hypothesis: Patients assigned to analgesic education are more satisfied with pain management after surgery as measured on a 0-10 Likert scale (where 0 means not satisfied at all and 10 means completely satisfied) on the third day after surgery.

*Secondary Aim 2:* To assess the effect of analgesic education on postoperative pain during the first 72 post-operative hours or until discharge (whichever is earlier)

Hypothesis. Patients assigned to analgesic education have lower time weighted average pain scores during the first 72 post-operative hours or until discharge (whichever is earlier).

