#### ***F. Measurements***

Demographics and comorbidities (*Table 1*) will be obtained from electronic medical reports. Blinded clinical evaluators will query patients for outcomes. Clinicians including nurses will be blinded to study and will be required to perform routine clinical management after surgery. Patients will be followed for outcomes daily for up to 72 hours after surgery. Any opioids prescriptions at discharge will be at the discretion of the primary care team. Long-term outcomes including modified brief pain inventory scores and the use of analgesics will be collected 90 days after surgery by telephone.

*Primary outcome* is opioid consumption during the initial 72 hours after surgery, will be collected from electronic medical records if discharged will be approached by phone and converted to morphine equivalent. Differences in morphine equivalents of 20% or more will be interpreted as clinically meaningful.

*Secondary Aim 1*; satisfaction with post-operative pain management will be evaluated using a 0-10 Likert scale (where 0 means not satisfied at all and 10 means

completely satisfied) on the third day after surgery by phone by blinded clinical evaluators. Difference of 2 points in satisfaction will be accepted as clinically meaningful difference.

**Secondary Aim 2;** pain scores will be obtained from electronic medical records which are recorded by nursing, in PACU it is every 15 minutes and in ward every 4 hours while hospitalized. Difference of 1.2 points in pain scores will be accepted as clinically meaningful difference.

**Exploratory Aim 1;** composite of opioid related side effects and the antiemetic use will be obtained from nursing and medication notes from electronic medical records.

**Exploratory Aim 2;** analgesic use will be obtained from the Ohio prescription

Sex
Age (years)
Ethnicity
Height (cm)
Weight (kg)
BMI
ASA status
Surgery Type
Smoking status (current, former, never)
Medical History : Pulmonary disease, Kidney disease, Hypertension, Diabetes Mellitus, Neurologic disease, Coronary Artery Disease, Myocardial infarction, Chronic pain conditions, illegal drug usage, alcohol abuse, previous surgery or stent placement and medication usage

registry at 3 months.

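### Low priority: Holm's procedure would replace plain Bonferroni for the two secondary outcomes with the same 5% family-wise error and never less power, though the gain is confined to one situation and to modest effects

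*Combined protocol and SAP*

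**What the plan says.** The Secondary Aims name two outcomes. The first is satisfaction: "To assess whether patients assigned to analgesic education (versus standard/generic) have better patient satisfaction with post-operative pain management". It is scored 0 to 10 on the third day. The second is time-weighted average pain over 72 hours or until discharge.

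Under Secondary Analysis, satisfaction "will be determined by using a t-test or linear regression adjusting for imbalanced covariates as appropriate", with a Wilcoxon or log-scale fallback if the scores are skewed. Pain "will be assessed in a manner similar to that for patient satisfaction scores". The multiplicity rule follows: "Adjusting for multiple testing using the Bonferroni correction, the secondary analyses will be carried out at the 97.5% confidence level", with the threshold written as 0.05/2. No step-down or gatekeeping rule appears, and no power is claimed for either secondary outcome.

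The Measurements section gives the effect sizes that the plan regards as important: "Difference of 2 points in satisfaction will be accepted as clinically meaningful difference" and "Difference of 1.2 points in pain scores will be accepted as clinically meaningful difference".

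One wording point: the opening of the statistical section says "The confidence level for all analyses is set at 95" percent, while the secondary rule uses 97.5%. The specific rule plainly governs, but the two sentences could be aligned.

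**The concern.** Under the current rule each secondary outcome faces 0.025 whatever the other shows. If pain gave P < 0.0001 and satisfaction gave P = 0.03, satisfaction would have to be called non-significant. Under Holm it would be significant, with no increase in the family-wise error. The plan therefore gives up some power without gaining any error control. What is at stake is the chance of confirming the second of the two outcomes once the first is established.

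**Working it through.** **Inputs from the documents.** Two secondary tests at 0.05/2; meaningful differences of 2 and 1.2 points; a fixed-design total of 588 (294 per arm); a final total of 1060 with 10% drop-out, so 530 × 0.90 = 477 evaluable per arm.

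**Assumptions, because the documents are silent.** Power of 70% or 80% for each outcome at 0.025; correlation between the two test statistics (both oriented towards benefit) of 0 or 0.5; SD of 2 to 5 for satisfaction and 1.5 to 3 for pain.

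**Step 1: the plan's own figures.**
- 0.05/2 = 0.025 is exact. With independent tests the family-wise error is 1 − 0.975² = 0.0494.
- Sidedness is not written. The plan states "assuming a CV of 1.00 we would need a total of 588 patients to have 90% power to detect a 20% decrease in opioid consumption". With SD on the log scale √ln(1 + 1.00²) = 0.8326, difference ln 0.80, two-sided 0.05 and 90% power, the normal formula gives 586 and the noncentral t gives 588. Two-sided testing is therefore the reading that reproduces the plan's number, and it is used below.

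**Step 2: error control.** In a simulation with 2,000,000 draws per scenario, the family-wise error with both nulls true was identical for Bonferroni and Holm: 0.0495 at correlation 0, 0.0466 at 0.5 and 0.0401 at 0.8. With one true effect and one null, the error on the null outcome under Holm was at most 0.0496.

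**Step 3: power.** The two-sided critical values are 2.241 (level 0.025) and 1.960 (level 0.05). The mean of each z statistic is d = 2.241 + z(power): 2.766 for 70% and 3.083 for 80%. Let B = P(both Z > 2.241) and X = P(Z₁ > 2.241, Z₂ > 1.960), from the bivariate normal. Then
- both significant, Bonferroni: B
- both significant, Holm: 2X − B
- power per outcome, Holm: power at 0.025 + (X − B)

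| Power each at 0.025 | Correlation | Both, Bonferroni (B) | X | Both, Holm | Gain (points) | Per outcome, Holm |
|---|---|---|---|---|---|---|
| 70% | 0 | 0.490 | 0.553 | 0.616 | 12.6 | 0.763 |
| 70% | 0.5 | 0.557 | 0.610 | 0.663 | 10.6 | 0.753 |
| 80% | 0 | 0.640 | 0.695 | 0.751 | 11.1 | 0.855 |
| 80% | 0.5 | 0.687 | 0.733 | 0.778 | 9.1 | 0.846 |

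The chance of at least one rejection is the same under both rules, for example 0.912 at 80% power and correlation 0.5. Holm acts only after one test has passed 0.025.

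**Step 4: which effects these powers correspond to.** 80% power at 0.025 needs a difference of 3.083 × √(2/n) SD.
- n = 477: 0.20 SD, which is 0.40 to 1.00 points of satisfaction (SD 2 to 5) and 0.30 to 0.60 points of pain (SD 1.5 to 3).
- n = 294: 0.25 SD, which is 0.51 to 1.27 and 0.38 to 0.76 points.

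All of these are below 2 and 1.2 points.

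**Step 5: power at the plan's meaningful differences.** The least favourable case is the largest SD, where 2/5 = 1.2/3 = 0.40 SD.
- n = 294: 0.9955 at 0.025 and 0.9981 at 0.05, a gap of 0.26 points.
- n = 477: 0.99996 and 0.99999.

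Holm cannot add more than this gap, because it tests no outcome at a level above 0.05.

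**The case against.** The strongest reply is that nothing here is wrong. The plan names the family, the method and the level, and the method is valid. A reader might infer that Bonferroni is a mistake, or that it costs power for nothing. The documents support neither. The plan expresses its rule as a confidence level, and Bonferroni supplies simple simultaneous 97.5% intervals that always agree with the tests. Holm has no equally simple matching intervals: an outcome with P = 0.03 could be declared significant while its 97.5% interval includes no difference. That objection stands and has to be disclosed in any replacement text.

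A second reply is that the gains in the step 3 table rest on powers that the plan does not state, and that they belong to effects the plan would not call meaningful. This also stands over the assumed SDs. It does not remove the point, because the plan tests for any difference and does not tie significance to the 2-point and 1.2-point thresholds, so a P value between 0.025 and 0.05 remains possible.

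A reader might also infer that success requires both outcomes. The introduction does link pain with satisfaction, but the Secondary Aims state two separate hypotheses and no rule requires both. The chance that both are significant is therefore a useful measure, not the plan's criterion.

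Finally, the document already records re-assessments at the second and third interim analyses. Relaxing a significance rule after those looks needs more justification than an ordinary wording change. That bears on the cost of the fix.

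**Conclusion.** The point holds as a cheap improvement of low priority, not as an error. That Holm controls the same 5% family-wise error and is never less powerful is a general result and depends on none of the assumptions. The size does depend on them: about 9 to 13 points for both outcomes significant and about 5 to 6 points per outcome if each has 70% to 80% power at 0.025 and the correlation is 0 to 0.5; under 0.3 points at the plan's meaningful differences for satisfaction SDs of 2 to 5 and pain SDs of 1.5 to 3. The power figures are for z- or t-tests and not for the Wilcoxon fallback.

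**What to change.** Before unblinding, by a dated amendment stating that the change was made without regard to interim results, replace the Bonferroni sentence under Secondary Analysis with:

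> The two secondary outcomes will be tested with the Holm procedure at a two-sided family-wise level of 0.05: the smaller P value against 0.025 and, only if significant, the other against 0.05. 97.5% confidence intervals will be shown for both; for the second outcome the interval may not match the step-down decision.

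No further patients, data or assumptions are needed. The costs are the amendment with its justification and the possible mismatch between interval and test for the second outcome. If the results have already been unblinded, or independence from the interim results cannot be stated, the prespecified Bonferroni rule should stay; it is valid.
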